3.1.2. Laboratory Data

Safety laboratory tests (hematology, chemistry, urine testing and other clinical laboratory tests) will be performed on Day 1 and Weeks 3, 6, 9, 12, 15, 18 and 24.

To determine if there are any clinically significant laboratory abnormalities, the safety tests will be assessed against the criteria specified in the sponsor reporting standards. The assessment will take into account whether each participant's baseline test result is within or outside the laboratory reference range for the particular laboratory parameter.

Baseline for all laboratory measurements is defined as the last result prior to dosing on Day 1.

3.1.3. Vital Signs

Vital sign measurements (blood pressure and pulse rate) will be taken on Day 1 and Weeks 3, 6, 9, 12, 15, 18 and 24.

Baseline is defined as the average of the triplicate measurements prior to dosing on Day 1.

Changes from baseline for supine systolic and diastolic blood pressure and pulse rate will be calculated for each post baseline timepoint.

The maximum decrease from baseline, over all measurements taken post-dose, will be calculated for supine systolic and diastolic blood pressures. The maximum increase from baseline, over all measurements taken post-dose, will be calculated for supine pulse rate.

The maximum increase from baseline will be calculated by first subtracting the baseline value from each post-dose measurement to give the change from baseline. The maximum of these values over the respective period will then be selected, except in the case where a participant does not show an increase. In such an instance, the minimum decrease should be taken. Similarly, the maximum decrease from baseline will be determined by selecting the minimum value of the changes from baseline. In cases where a participant does not show a decrease, the minimum increase should be taken.

3.1.4. Electrocardiogram (ECG)

Standard 12-lead ECG (including heart rate, QT, QTcF, PR and QRS interval) will be obtained on Day 1 and Weeks 3, 6, 9, 12, 15, 18 and 24.

Baseline is defined as the average of the triplicate results prior to dosing on Day 1.

Change from baseline for heart rate, QT, QTcF, PR and QRS interval will be calculated for each post baseline timepoint.

The maximum absolute value (post-dose) and the maximum increase from baseline over all measurements taken post-dose will be calculated for QTcF, PR and QRS.

The maximum increase from baseline will be calculated by first subtracting the baseline value from each post-dose measurement to give the change from baseline. The maximum of these values over the respective period will then be selected, except in the case where a participant does not show an increase. In such an instance, the minimum decrease should be taken.

3.2. Secondary Endpoint(s)

- *Serum unbound and total trough concentrations (C_{trough}) of PF-06946860 at Weeks 3, 6, 9, 12 and 15.*

Serum concentrations of unbound and total PF-06946860 will be collected both pre- and post-dose on Day 1 and at Week 12, pre-dose only at Weeks 3, 6 and 9, and additionally at Weeks 1, 2, 4, 5, 13, 14, 15, 18 and 24.

Trough concentrations (C_{trough}) are defined as the samples measured pre-dose at Weeks 3, 6, 9 and 12, and at Week 15. Dose normalized C_{trough} will also be calculated, if appropriate.

3.3. Other Endpoint(s)

3.3.1. Immunogenicity (ADA, NAb)

- *Incidence of ADA and NAb, if applicable.*

ADA and NAb, if applicable, will be assessed on Day 1 and Weeks 2, 3, 6, 9, 12, 15, 18 and 24.

Baseline is defined as the pre-dose result on Day 1.

3.3.2. Pharmacodynamics (GDF-15)

- *Serum concentrations of total and, if feasible, unbound GDF-15 at time points specified in the schedule of activities (SoA) in the protocol.*

Serum concentrations of total and, if feasible, unbound GDF-15 will be measured both pre- and post-dose on Day 1 and Week 12, pre-dose only at Weeks 3, 6 and 9, and additionally at Weeks 1, 2, 4, 5, 13, 14, 15, 18 and 24.

Baseline is defined as the pre-dose result on Day 1. Trough timepoints are pre-dose at Weeks 3, 6, 9 and 12, and Week 15.

Change from baseline, relative change from baseline (i.e. post-dose / baseline) and percent change from baseline for total and, if feasible, unbound GDF-15, will be calculated for each post baseline timepoint. The maximum, maximum percent change from baseline and time to maximum, for total GDF-15 may also be calculated for each participant.

3.3.3. Efficacy

- *Change from baseline LSMI measured by CT scan at time points specified in the schedule of activities (SoA) in the protocol.*

Lumbar Skeletal Muscle Index (LSMI), measured by CT Scan, will be collected at Screening (Baseline) and Weeks 6 and 12. Change from baseline will be calculated for each post baseline timepoint.

- *Change from baseline body weight at time points specified in the schedule of activities (SoA) in the protocol.*

Body Weight will be collected on Day 1 (Baseline) and Weeks 3, 6, 9, 12, 15, 18 and 24.

Change from baseline and percent change from baseline will be calculated for each post baseline timepoint.

3.3.4. Patient-Reported Outcomes (PRO)

PRO data will be collected for Cohort 1 only.

CCI

[REDACTED]

[REDACTED]

[REDACTED]

[REDACTED]

[REDACTED]

3.3.4.2. PRO CTCAE Items

- *Change from baseline scores for selected PRO-CTCAE items at time points specified in Table 2 in the protocol.*

Data will be collected on Day 1 (Baseline) and Weeks 3, 6, 9, 12 and 18 using a 5-point scale.

Change from baseline will be calculated for each post baseline timepoint.

3.3.4.3. PROMIS Fatigue – Short Form 7a

- *Change from baseline score for PROMIS-Fatigue at time points specified in Table 2 in the protocol.*

Data will be collected on Day 1 (Baseline) and Weeks 6, 12, and 18 using a 5-point scale.

The PROMIS Fatigue Short Form 7a has seven questions, each with five response options ranging in value from 1 to 5. A total raw score will be calculated as the sum of the responses to all seven questions.

The total raw score will then be translated into a T-score for each participant using the Fatigue 7a Short Form score conversion table, provided in Appendix 1.1. The T-score rescales the raw score into a standardized score with a mean of 50 and a standard deviation (SD) of 10.

Change from baseline for PROMIS-Fatigue T-score will be calculated for each post baseline timepoint.

3.3.4.4. PROMIS Physical Function – Short Form 8c

- *Change from baseline score for PROMIS-Physical Function at time points specified in Table 2 in the protocol.*

Data will be collected on Day 1 (Baseline) and Weeks 6, 12, and 18 using a 5-point scale.

The PROMIS Physical Function Short Form 8c has eight questions each with five response options ranging in value from 1 to 5. A total raw score will be calculated as the sum of the responses to all eight questions.

The total raw score will then be translated into a T-score for each participant using the Physical Function 8c Short Form score conversion table, provided in Appendix 1.1. The T-score rescales the raw score into a standardized score with a mean of 50 and a standard deviation (SD) of 10.

Change from baseline for PROMIS-Physical Function T-score will be calculated for each post baseline timepoint.

3.3.4.5. FAACT Total and Sub Scale Scores

- *Change from baseline FAACT total and sub-scale scores at time points specified in Table 2 in the protocol.*

Data will be collected on Day 1 (Baseline) and Weeks 6, 12, and 18 using a 5-point scale.

See Appendix 1.2 for FAACT scoring guidelines showing the calculation of FAACT subscales and two total scores.

Additionally, FAACT-5IASS (FAACT 5-item Anorexia Symptoms Subscale) will be calculated (using only items C6, ACT6, ACT7, ACT10 and ACT3, and a similar scoring system as for the other sub-scales): -

1. Add up the scores (with or without reversing)
2. Multiply by 5
3. Divide by the number of items answered

Change from baseline for FAACT total scores and subscales (including 5IASS) will be calculated for each post baseline timepoint.

3.3.4.6. PGI-S

- *Change from baseline PGI-S at time points specified in Table 2 in the protocol.*

Data will be collected on Day 1 (Baseline) and Weeks 3, 6, 9, 12 and 18 using a 5-point scale.

Change from baseline will be calculated for each post baseline timepoint.

3.3.4.7. PGI-C

[figure not shown]
- *PGI-C at time points specified in Table 2 in the protocol.*

Data will be collected at Weeks 12 and 18 using a 7-point scale.

[figure not shown]
[figure not shown]
Categories will be combined to produce a 5-point scale as defined below:-

Category	Definition
Much Better	1
Somewhat Better	2-3
No Change	4
Somewhat Worse	5-6
Much Worse	7

CCI

CCI

3.3.6. Completion of Anti-Tumor Treatment

- *Number and % of participants completing anti-tumor treatment as originally prescribed.*

Information regarding each participant's anti-tumor treatment (e.g. change of dose) will be collected.

3.3.7. Number and % of Participants Alive at LSLV

- *Number and % of participants alive at last subject last visit (LSLV).*

Any deaths during the study will be collected.

3.3.8. RECIST 1.1 Categorization

- *The RECIST 1.1 (overall) categorization using CT scan at time points specified in the schedule of activities (SoA) in the protocol.*

Data will be collected at Screening (Baseline) and Weeks 6 and 12.

3.4. Baseline Variables

N/A

3.5. Safety Endpoints

See Section 3.1 for details.

4. ANALYSIS SETS (POPULATIONS FOR ANALYSIS)

Data for all participants will be assessed to determine if participants meet the criteria for inclusion in each analysis population prior to unblinding and releasing the database and classifications will be documented per standard operating procedures.

Population	Description
Enrolled/Randomly assigned to investigational product	
“Enrolled” means a participant’s, or their legally authorized representative’s, agreement to participate in a clinical study following completion of the informed consent process.
 
Potential participants who are screened for the purpose of determining eligibility for the study, but do not participate in the study, are not considered enrolled, unless otherwise specified by the protocol

Evaluable	All participants randomly assigned to investigational product and who take at least 1 dose of investigational product
Safety	All participants randomly assigned to investigational product and who take at least 1 dose of investigational product
PK	All randomized participants who received a dose of PF-06946860 and in whom at least 1 serum concentration value is reported
PD	All randomized participants who received a dose of PF-06946860 and in whom at least 1 serum GDF-15 concentration is reported
Immunogenicity	All randomized participants who received a dose of PF-06946860 with at least 1 ADA result reported
Efficacy	All participants randomly assigned to investigational product and who take at least 1 dose of investigational product

5. GENERAL METHODOLOGY AND CONVENTIONS

5.1. Hypotheses and Decision Rules

There is no statistical hypothesis testing planned for this study and no statistical decision rules will be applied.

5.2. General Methods

Unless otherwise stated, all summaries and plots will be presented by treatment, if appropriate.

5.2.1. Analyses for Continuous Endpoints

Unless otherwise stated, continuous variables will be presented using summary statistics: number of observations, arithmetic mean, standard deviation, median, minimum and maximum values.

5.2.2. Analyses for Categorical Endpoints

Categorical variables will be presented using summary statistics: number of observations and percentages.

5.3. Methods to Manage Missing Data

For the analysis of safety endpoints, the sponsor data standard rules for imputation will be applied.

In all PK data presentations (except listings), concentrations below the limit of quantification (BLQ) will be set to zero.

In all PD data presentations (except listings), BLQ concentrations will be set to the lower limit of quantification (LLOQ).

In listings, BLQ values will be reported as “<LLOQ”, where LLOQ will be replaced with the value for the LLOQ.

For PK and PD summary tables and plots of mean/median profiles, statistics will be calculated having set concentrations to missing if one of the following cases is true: -

1. A concentration has been collected as ND (ie not done) or NS (ie no sample),
2. A deviation in sampling time is of sufficient concern or a concentration has been flagged anomalous by the pharmacokineticist/statistician.

CCI

6. ANALYSES AND SUMMARIES

6.1. Primary Endpoint(s)

6.1.1. Adverse Events

Adverse events will be summarised by treatment and overall and in accordance with sponsor reporting standards using the safety population defined in Section 4.

Incidence and CTCAE grade of treatment emergent adverse event (TEAE) tables will additionally be produced ('All causality' and 'Treatment related', separately) to summarise the total number of adverse events by preferred term, which will be reported by treatment and overall.

6.1.2. Laboratory Data

Laboratory data will be listed and summarized by treatment, in accordance with the sponsor reporting standards using the safety population defined in Section 4. Baseline is as defined in Section 3.1.2.

6.1.3. Vital Signs

Absolute values and changes from baseline in supine systolic and diastolic blood pressure and pulse rate will be summarised by treatment and time point, according to sponsor reporting standards using the safety population defined in Section 4. Baseline is as defined in Section 3.1.3.

Individual plots of change from baseline systolic and diastolic blood pressure and pulse rate, versus time, will be produced with all participants on the same plot, paged by treatment. Separate colours will be used for each participant with a black solid line added for the mean. Maximum decrease from baseline for supine systolic and diastolic blood pressures and maximum increase from baseline for supine pulse will be summarised by treatment, according to sponsor reporting standards.

Maximum absolute values and changes from baseline for supine vital signs will also be summarised descriptively by treatment using categories as defined in Appendix 4. Numbers and percentages of participants meeting the categorical criteria will be provided. All planned and unplanned post dose time points will be counted in these categorical summaries. All values meeting the criteria of potential clinical concern will be listed.

6.1.4. Electrocardiogram (ECG)

Absolute values and changes from baseline in QT, heart rate, QTcF, PR and QRS will be summarised by treatment and time point using sponsor reporting standards using the safety population defined in Section 4. Tables will be paged by parameter. Baseline is as defined in Section 3.1.4.

Individual plots of change from baseline QT, heart rate and QTcF, versus time, will be produced with all participants on the same plot, paged by treatment. Separate colours will be used for each participant with a black solid line added for the mean. Maximum increase from baseline for QTcF will be summarised by treatment, according to sponsor reporting standards.

Maximum absolute values and changes from baseline for QTcF, PR and QRS will also be summarised descriptively by treatment using categories as defined in Appendix 4. Numbers and percentages of participants meeting the categorical criteria will be provided. All planned and unplanned postdose timepoints will be counted in these categorical summaries. All values meeting the criteria of potential clinical concern will be listed.

Listings of participants with any single post dose value > 500 msec will also be produced for QT.

6.2. Secondary Endpoint(s)

Presentations for serum unbound and total PF-06946860 concentrations for participants in the PK population (as defined in Section 4) will include: -

- A listing of all concentrations sorted by dose, participant ID, and nominal time point. The concentration listing will also include the actual times.
- Individual concentration-time plots (semi-log scale) by dose using actual time post first dose. There will be separate spaghetti plots for each dose. All timepoints will be included and trough timepoints may be highlighted, e.g. using symbols.
- A summary of all concentrations by dose and nominal time point, where the set of statistics will include n, mean, standard deviation, coefficient of variation (CV, %),

median, minimum, maximum and the number of concentrations at or above the lower limit of quantification (NALQ).

- A summary of C_{trough} and dose normalized C_{trough} , if appropriate, by dose and nominal time point, where the set of statistics will include n, arithmetic mean, standard deviation, CV (%), median, geometric mean, geometric CV (%), Q1, Q3, minimum, maximum, and NALQ.
- Median concentration-time plot (semi-log scale, all timepoints) by dose using nominal time (all doses on the same plot).
- Median trough concentration-time plot (linear scale) by dose using nominal time (all doses on the same plot), individual concentrations may be included.
- Mean trough concentration-time plot (linear scale) by dose using nominal time (all doses on the same plot), individual concentrations may be included.

No formal inferential statistics will be applied to the pharmacokinetic data.

Additional PK analyses may be performed if deemed appropriate, and may not be included in the CSR.

6.3. Other Endpoint(s)

6.3.1. Immunogenicity (ADA, NAb)

Immunogenicity analyses will be performed on the immunogenicity analysis set defined in Section 4. Definitions for ADA and NAb terms are defined in Appendix 2. Immunogenicity analyses will include: -

- A listing of ADA and NAb results for all participants and if appropriate, a listing of ADA and NAb data, including onset, titer, and if appropriate, duration (number of days participant is ADA positive or NAb positive) for all ADA-positive participants.
- A summary of the incidence of ADA and NAb by dose and all doses combined.
- A summary of the percentage of participants who are ADA positive and NAb positive by time and by dose and all doses combined. The cumulative % of ADA-positive and NAb-positive participants may also be included.
- If appropriate, spaghetti plots of individual participant ADA and NAb titer by dose
- If appropriate (e.g. the number of ADA-positive participants for each dose is ≥ 3), a summary of ADA and NAb titer by time for each dose.

6.3.2. Pharmacodynamics (GDF-15)

All PD analyses will be performed on the PD population as defined in Section 4. Baseline is as defined in Section 3.3.2.

Presentations for total and/or unbound (as data permit) GDF-15 concentrations will include: -

- A listing of all concentrations (absolute values, change from baseline, relative change from baseline and percent change from baseline) sorted by treatment (dose), participant ID and nominal time point. The listing will also include the actual times. The maximum,

maximum percent change from baseline and time to maximum, for total GDF-15 may also be included.

- Individual concentration-time plots (for absolute values and percent change from baseline) by treatment using actual time. There will be separate spaghetti plots for each treatment. All timepoints will be included and trough timepoints may be highlighted, e.g. using symbols.
- A summary of concentrations (absolute values and percent changes from baseline) by treatment and nominal time point, where the set of statistics will include n, mean, standard deviation, CV (%), minimum, Q1, median, Q3, maximum, and geometric mean, geometric CV (%) and NALQ (for absolute values only).
- Median concentration-time plot (for absolute values and percent change from baseline) by treatment using nominal time (all treatments on the same plot), individual concentrations may be included on the plot.
- A summary of the maximum, maximum percent change from baseline and time to maximum, for total GDF-15 may be produced.

Relative change from baseline (i.e. post-dose / baseline) unbound GDF-15 concentration at Week 4 may also be modelled (as data permit), if appropriate. The analysis will be performed on the log scale using an analysis of covariance with log baseline and treatment as fixed terms in the model. Back transformed least squares means (and 80% confidence intervals) will be obtained for each treatment. Plots of these back-transformed LS means (including 80% CIs) will also be produced (all treatments on the same plot with different colours/symbols for each treatment). The relative changes will be presented as percent change from baseline ($[\text{relative change from baseline} - 1] * 100$).

If this analysis is deemed inappropriate (e.g. due to a large number of data below the level of quantification), the analysis may not be performed, or may be replaced by an alternative analysis.

Additional PD, and/or population PK/PD, analyses may be performed if deemed appropriate, and will not be included in the CSR.

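### SAP 6.3.2 reports an arithmetic CV(%) for percent change in GDF-15, where it is not a valid statistic, and gives no group summary of the post/baseline ratio

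*SAP*

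**What the plan says.** SAP 3.3.2 derives three post-baseline quantities: "Change from baseline, relative change from baseline (i.e. post-dose / baseline) and percent change from baseline for total and, if feasible, unbound GDF-15".

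SAP 6.3.2 then plans "A summary of concentrations (absolute values and percent changes from baseline) by treatment and nominal time point". The statistics are n, mean, SD and CV(%), followed by "minimum, Q1, median, Q3, maximum, and geometric mean, geometric CV (%) and NALQ (for absolute values only"). Mean, SD and CV(%) therefore apply to percent change as well as to concentrations, while the geometric statistics and the count of quantifiable values (NALQ) apply to concentrations alone. The ratio appears in the listing but in no descriptive table.

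The same section has an optional model: "Relative change from baseline (i.e. post-dose / baseline) unbound GDF-15 concentration at Week 4 may also be modelled (as data permit), if appropriate". It is a log-scale ANCOVA with log baseline and treatment, back-transformed with 80% intervals. "The relative changes will be presented as percent change from baseline", that is, as (ratio - 1) x 100. It may be dropped or replaced, for example if many values fall below quantification.

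SAP 5.3 adds: "In all PD data presentations (except listings), BLQ concentrations will be set to the lower limit of quantification (LLOQ").

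**The concern.** A CV describes spread relative to the mean. It needs a positive quantity with a true zero. Percent change from baseline has neither: it runs from -100% upward, and its zero means only that nothing changed. Dividing its SD by its mean gives a negative number under suppression, a very small one when suppression is deep, and an arbitrary one when the mean change is close to zero.

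The ratio behind the percent change is positive, suits the log scale, and is already calculated. Because it has no group summary, the only mean of percent change in the table is arithmetic. Where the Week 4 model is run, a geometric mean appears in the same unit, and the SAP labels neither. With about 6 evaluable participants per cohort (SAP 2.2), a reader could take the CV for a measure of between-patient consistency, or wonder why two mean percent changes differ.

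**Working it through.** **Inputs.** The statistics list and model are those of SAP 6.3.2; n = 6 is from SAP 2.2. The documents give no on-treatment GDF-15 values and no figure to reproduce. *Assumption:* the ratio is lognormal with geometric mean g (0.05 to 10 shown) and geometric CV c (30% to 100%).

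**Formulas.**
- Arithmetic mean percent change = 100 x (g x sqrt(1 + c²) - 1)
- SD of percent change = 100 x g x c x sqrt(1 + c²)
- CV(%) of percent change = 100 x SD / mean
- Log-scale (geometric) percent change = 100 x (g - 1)
- Gap, arithmetic minus geometric = 100 x g x (sqrt(1 + c²) - 1)

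**Step 1: population values for c = 30% to 100%.**

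| g | Geometric change | CV(%) of percent change | Gap (points) |
|---|---|---|---|
| 0.05 | -95% | -2 to -8 | 0.2 to 2.1 |
| 0.1 | -90% | -3 to -16 | 0.4 to 4.1 |
| 0.5 | -50% | -33 to -241 | 2.2 to 20.7 |
| 0.9 | -10% | -467 at c = 30%; +8075 at c = 50%; +467 at c = 100% | 4.0 to 37.3 |
| 10 | +900% | 33 to 108 | 44 to 414 |

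Worked entry, g = 0.9 and c = 0.5: 0.9 x sqrt(1.25) = 1.0062, so the mean is +0.62% and the SD is 50.3 points. The CV is about 8075%. At g = 10 the CV is close to that of the ratio itself (30 to 100%), so for large rises it does little harm.

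**Step 2: samples of six (100,000 simulated).** At g = 0.9, c = 50%, the sample CV has a 5th to 95th percentile range of -1694% to +1745% and is negative in 53% of samples. The arithmetic and geometric changes differ in sign in 17.5% of samples, and in 25.5% at c = 80%. At g = 0.05 (c = 50% or 80%) the signs never differ.

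**Step 3: two illustrative sets (not trial data).**
- Ratios 0.4, 0.5, 0.7, 0.9, 1.4, 2.2: mean change +1.7%, SD 67.9, CV 4077%, median -20.0%. The geometric mean ratio expressed as a change is -14.6%, and the CV of the ratios is 66.8%. A geometric mean of the percent changes cannot be computed, because four of the six are negative.
- Residual fractions 1, 2, 3, 5, 10, 15%: mean change -94.0%, SD 5.4, CV -5.8%. The geometric mean change is -95.9% and the geometric CV of the ratio 134%. The gap is 95.9 - 94.0 = 1.9 points.

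**Step 4: table mean against the Week 4 model.** With one treatment, the model's LS mean at the mean log baseline equals the mean log ratio. In a six-value check both gave 0.0924, against an arithmetic mean ratio of 0.0991. On the same participants, the table mean therefore lies above the model estimate whenever the ratios vary.

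**Step 5: values below quantification.** If a post-dose value is set to the LLOQ, its log ratio is log(LLOQ) - log(baseline). If every value at a visit is so set, the SD of the log ratio equals the SD of log baseline, and the geometric CV says nothing about residual target.

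**The case against.** The strongest reply is that little is hidden. The same table prints minimum, quartiles, median and maximum of percent change. The group plot is a median plot, individual percent-change plots are planned, and every participant's ratio is listed. Under a lognormal ratio the median percent change targets the same quantity as the log-scale estimate. All of this stands.

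It also answers several stronger readings that a reader might infer:

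- *That confining geometric statistics to absolute values is an error.* It is not, since they cannot be computed on negative changes. What is missing is a summary of the ratio.
- *That the CV conceals the spread, or one patient dictates the result.* In the residual-fraction example the range row would show -99% to -85%, and the median is printed beside the mean.
- *That the table and the Week 4 model contradict each other.* They are different summaries. The model is optional and covers unbound GDF-15 at one visit.
- *That the number below quantification goes unreported for percent change.* NALQ is already printed for absolute values at the same visits. Apart from missing baselines, repeating it would duplicate the count.

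The reply does not make the CV valid, nor does it give a reason to omit a summary of a ratio already derived.

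**Conclusion.** The point holds as a defect of presentation. CV(%) should not be printed for percent change: it is a small negative number under deep suppression, unstable when the mean change is near zero, and roughly usable only for large rises. The missing ratio summary leaves an unlabelled arithmetic mean beside a possible unlabelled geometric one. At Week 4 they would differ by about 0.2 to 4 points if unbound GDF-15 is suppressed by 90-95%, and by more under weaker suppression. These sizes rest on the lognormal assumption and the assumed geometric CVs of 30-100%.

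A reader might infer that a proof-of-mechanism conclusion is at risk. The documents do not support that. GDF-15 is a tertiary/exploratory endpoint (SAP 2.1), and SAP 5.1 plans no hypothesis test or decision rule. The version history (SAP Table 1) mentions output for a POM declaration without expanding the term or giving a criterion that uses the mean or CV. No trial conclusion is shown to change.

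**What to change.** In SAP 6.3.2:

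1. Drop CV(%) for percent change.
2. Add the geometric mean and geometric CV of the post/baseline ratio by treatment and nominal time, with the geometric mean shown as (ratio - 1) x 100, the conversion the Week 4 model already uses.
3. Keep the median, quartiles and range of percent change.
4. Label the table mean arithmetic and the Week 4 estimate geometric.

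The cost is SAP wording and a table shell, with no new data. There is one downside. Where many unbound values are set to the LLOQ, the ratio is only a bound on suppression and its geometric CV partly reflects baseline spread. At those visits, read the ratio summary with the NALQ already printed for absolute values, or omit it.
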